8.2. Secondary Objectives

To estimate the overall proportion of domperidone prescriptions before and after implementation of the risk minimisation measures for domperidone for each of the components of the composite endpoint individually, the time trend of apparent indication, and days supplied (\leq 7 days vs. >7 days), and the age and sex of the people receiving prescriptions.

9. **RESEARCH METHODS**

9.1. Study Design

This is a post-authorisation, retrospective, observational cohort study using pre- and postdesign to examine the changes in the prescribing patterns.

A cohort of patients prescribed domperidone will be identified from the following existing secondary data sources: CPRD for the United Kingdom and IMS databases for France, Germany, Belgium, and Spain. The countries are selected to include countries with relatively high per capita use of domperidone and at least 1 country with relatively low per capita use of domperidone as well as the availability of robust longitudinal electronic medical records databases in those countries. These data sources include information on prescriptions written, patient demographics, and diagnosis.

9.2. Setting and Study Population

9.2.1. Study Setting and Population

The study population will be defined as all patients receiving domperidone in the outpatient setting during the pre-defined periods (pre- and post- implementation periods of the risk minimisation activity) in the selected European Union countries (France, Germany, United Kingdom, Belgium, and Spain). Patients will be included in the study cohort if they have at least 1 prescription for domperidone in the selected databases during the pre-defined periods, and have membership or have been registered with the practice and have available medical history for at least 180 days before the domperidone prescription.

The date of the first prescription of domperidone in the pre-defined study periods will be defined as the index date. Patients will be followed from the index date to the earliest of the following dates:

- end of the study period;
- transfer out of the practice; or
- end of the practice's qualification as up to standard (a designation used in some databases to differentiate between practices that meet a data standard and those who do not for databases, such as CPRD).

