9.2.2. Study Period

The study period will be divided into a background period and pre- and post- implementation periods of risk minimisation measures as follows:

- A background period (1 January 2011 through 31 March 2013)
- A 1-year pre-implementation period of risk minimisation measures (1 April 2013 through 31 March 2014)
- A 1-year post-implementation period of risk minimisation measures (1 October 2014 through 30 September 2015)

The period during which the label change took place and the DHPC was sent will be used as the period during which the risk minimisation measures were implemented (1 April 2014 through 30 September 2014).

Because the amendments to the product information were suggested by the PhVWP in October 2011, the study will track prescribing pattern changes from 1 January 2011 (a time that preceded most of the discussion and implementation of the label changes, i.e., a background period) through 30 September 2015.

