9.7. Data Analysis

Data analysis in the study will be descriptive. Continuous variables will be presented using appropriate descriptive statistics, such as mean, median, standard deviation and range. Categorical variables will be presented using percent and frequency tables. The rates and 95% CI of all study endpoints (i.e., risk minimisation indicators) will be calculated for the 2011-2015 period, using quarterly time blocks for the pre- and post- risk minimisation implementation periods. The rates will be calculated per 1000 domperidone-treated patients or as percentage of domperidone prescriptions, as appropriate. Paediatric data will be described separately from adult patients and rate of paediatric use will be calculated as fraction of overall domperidone utilisation. Missing values will be reported as missing and no imputation will be undertaken. All data analysis will be done in SAS using the version that is current when the analyses are done.

The rates for the primary endpoints of the study (the proportion of all prescriptions that are consistent with the revised label) will be calculated 4 ways to address uncertainty about 1) Unknown indication (is it assumed to be nausea and vomiting and therefore on-label, or is it assumed to be some other indication and therefore off-label) and 2) Duration of use that may be shorter than the days' supply (prescriptions with more than 7 days' supply assumed to

be intended for ≤ 7 days use, and provision of additional tablets for possible future episodes, and therefore on-label, versus assumed to be for >7 days use and therefore off –label):

- 1. Unknown indication assumed to be nausea and vomiting. Duration assumed to be ≤ 7 days (most optimistic scenario) meets the following conditions:
 - a. Prescription for nausea and vomiting or unknown indication but no recent diagnosis of GERD, gastroparesis, IBS, symptoms of postural hypotension in Parkinson patients, or as an aid to lactation;
 - b. Dose no higher than recommended;
 - c. No prescription to patients with certain cardiac and hepatic conditions; and
 - d. No co-prescription with CYP3A4 inhibitors or QT-prolonging drugs. (This considers such contraindicated co-medications only when they were prescribed ≤ the date of the domperidone prescription.)
- 2. Unknown indication assumed to be an off-label indication, duration assumed to be \leq 7days (an intermediate scenario) meets the following conditions:

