9.9. Limitations of the Research Methods

9.9.1. Strengths

- The study will use longitudinal real-life data on the utilisation of domperidone in different European countries with a pre- and post- study design to measure the effectiveness of the risk minimisation activities and examine changes on prescribing patterns. Data on prescription patterns prior to the label change provide a useful comparator for the prescription patterns observed after the label change.
- The data from this study are not collected by specific consent of patients or prescribers and thus are not subject to volunteer and reporting bias.
- All prescriptions for eligible patients that are captured by the database will be included, providing a robust sample size and a statistically-reliable estimate of compliance with the new domperidone label.
- Data on prescription patterns prior to the label change provide a useful comparator for the prescription patterns observed after the label change and distribution of the DHPC. Thus this study provides an opportunity to demonstrate not only the final outcomes of the implemented risk minimisation measures, but also to demonstrate the effectiveness of the implementation process by comparing the endpoints "before" and "after" the implementation.
- Using the combination of the prescribers' survey and healthcare database analysis, the extent of domperidone on-label vs. off-label prescription will be assessed both in terms of process indicators (investigated through survey) and outcome indicators (investigated through database analysis). This should provide a comprehensive view of the effectiveness of domperidone risk minimisation measures.

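### Section 9.2.1 admits patients only through the pre- and post-implementation years, which contradicts the tracking from January 2011 promised in 9.2.2 and leaves 11 of 19 quarters empty or selected

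*Protocol*

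**What the plan says.** Protocol section 9.2.1 defines the population as "all patients receiving domperidone in the outpatient setting during the pre-defined periods (pre- and post- implementation periods of the risk minimisation activity", and the abstract repeats this. A patient enters with "at least 1 prescription for domperidone in the selected databases during the pre-defined periods" and at least 180 days of prior history. The section goes on: "The date of the first prescription of domperidone in the pre-defined study periods will be defined as the index date". Then: "Patients will be followed from the index date to the earliest of the following dates", namely the end of the study period, transfer out, or loss of the practice's data-quality status.

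Section 9.2.2 gives each period its own dates. It lists "A background period (1 January 2011 through 31 March 2013", then the pre-implementation year (1 April 2013 to 31 March 2014) and the post-implementation year (1 October 2014 to 30 September 2015). The implementation period is set apart as 1 April to 30 September 2014. The section then states that "the study will track prescribing pattern changes from 1 January 2011" through 30 September 2015, because that start precedes most of the discussion of the label changes.

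Section 9.7 says that rates with 95% confidence intervals for all endpoints "will be calculated for the 2011-2015 period, using quarterly time blocks". The sentence continues by attaching those blocks to the pre- and post-implementation periods. Section 8.2 makes the time trend of apparent indication and days supplied a secondary objective. Section 9.5 analyses prescriptions from the study period that meet the inclusion criteria. Section 9.9.1 says: "All prescriptions for eligible patients that are captured by the database will be included".

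**The concern.** The entry rule names two of the four periods. A patient prescribed domperidone only between January 2011 and March 2013, or only between April and September 2014, never meets it. For admitted patients, everything before the index date lies outside follow-up. The protocol nevertheless wants the background period as the picture of prescribing before the label discussion, and the implementation period as the transition.

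At stake is the descriptive time series: the 2011-2015 rates and the trend objective in 8.2. Section 9.6 leaves extraction to each supplier's standard practice. An ambiguous entry rule could therefore be applied differently in different databases, giving country series that are not comparable.

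**Working it through.** The plan states no figure on this point, so there is none to reproduce. The check applies the 9.2.1 rules to the 9.2.2 dates.

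**Step 1: count the quarters (months divided by 3).** Background 27/3 = 9; pre-implementation 12/3 = 4; implementation 6/3 = 2; post-implementation 12/3 = 4. The total is 57/3 = 19.

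**Step 2: apply entry, index date and follow-up.** With the periods as dated, the earliest possible index date is 1 April 2013.

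| Period | Quarters | 9.2.1 as written | If all prescriptions of cohort members are used (9.9.1) |
|---|---|---|---|
| Background | 9 | No patients | Only patients prescribed again in the pre or post year |
| Pre | 4 | All eligible patients | All eligible patients |
| Implementation | 2 | Only patients already indexed in the pre year | Only patients also prescribed in the pre or post year |
| Post | 4 | All eligible patients | All eligible patients |

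Unselected quarters: 4 + 4 = 8 of 19. Outside the entry periods: 9 + 2 = 11 of 19. Under the written rule, someone first prescribed in April to September 2014 is either excluded or indexed only at a later post-year prescription.

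**Step 3: primary comparison.** The risk ratio in 8.1 uses only the pre year and the post year. Each admits everyone prescribed in it, subject to the history rule, so the ratio does not change.

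**Step 4: what selection could do on the second reading.** Let r be the share of background prescriptions that belong to returning patients, and d the compliance among those kept minus that among those dropped. Then observed minus true compliance = (1 - r) x d. The documents give neither r nor d, so the following values are assumptions.

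- Assume 60% of background prescriptions go to episodic users (70% compliant, 10% return) and 40% to long-term users (20% compliant, 80% return). True compliance is 0.6 x 0.7 + 0.4 x 0.2 = 0.50. Then r = 0.06 + 0.32 = 0.38, and the kept group shows (0.06 x 0.7 + 0.32 x 0.2)/0.38 = 0.279. The dropped group has (0.54 x 0.7 + 0.08 x 0.2)/0.62 = 0.635, so d = -0.356 and the shift is 0.62 x (-0.356) = -0.22.
- Swap the two compliance values. True compliance is 0.6 x 0.2 + 0.4 x 0.7 = 0.40, and the kept group shows (0.06 x 0.2 + 0.32 x 0.7)/0.38 = 0.62. The sign reverses.
- With equal compliance in both groups, d = 0 and there is no shift.
- In a simulation in which each patient's prescribing rate stays constant (gamma-distributed, shape 0.3, mean 0.5, 1 or 2 prescriptions a year), r is 0.85, 0.93 or 0.97. With d = -0.356 the shifts are about -0.05, -0.02 and -0.01. This model has no stopping of use, so it favours a high r.

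The range runs from no shift to about 22 points in either direction. It shows only that the selection could matter, not that it does.

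**The case against.** The strongest reply is that this is loose wording and the intent is plain. The index-date sentence speaks of study periods, and 9.2.2 counts the background among the parts into which the study period is divided, so an index date in 2011 can be read into the text. Section 9.7 attaches its quarterly blocks to the pre- and post-implementation periods. If that phrase loosely means before and after across 2011-2015, the similar parenthesis in 9.2.1 could mean the same. If it is strict, 9.7 promises quarterly blocks only for the two single years and does not by itself require 19 quarters.

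Much of this stands. Section 9.7 alone does not prove the contradiction, and the intent to include 2011 onwards is clear. But the conflict between 9.2.1 and 9.2.2 remains. Section 9.2.2 gives the pre-implementation year its own dates, separate from the background, and nothing in the protocol admits patients prescribed only in April to September 2014.

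A reader might also infer that the series will show an artificial step at April 2013, or that every trend drawn from it is biased. The documents do not support either. A step arises only if the entry rule is applied strictly while the forward-only follow-up rule is ignored; applied together, the two rules leave an obvious gap. The 8 pre and post quarters are unselected on every reading. Nor do the documents say that one-off users are more often on-label than repeat users, so no direction can be assigned. Finally, a prescription-level endpoint is not the whole story, since 9.7 also allows rates per 1000 treated patients.

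**Conclusion.** The point holds as an internal contradiction. The entry, index-date and follow-up rules in 9.2.1 and the abstract defeat the tracking that 9.2.2 promises, and they undercut the 2011-2015 rates in 9.7 and the trend objective in 8.2. Taken literally, 9 of 19 quarters are empty and 2 hold only patients carried over from the pre year. On the alternative reading the same 11 quarters hold patients selected by use in another period, with an effect on compliance of unknown size and sign.

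This rests on reading pre- and post-implementation as 9.2.2 dates them. The primary risk ratio and the pre-versus-post component comparisons are untouched. The protocol should be corrected before extraction, but the main result is not at risk.

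**What to change.** In 9.2.1 and the abstract, define cohort entry and the index date over the whole study period, 1 January 2011 through 30 September 2015, naming the background, pre-implementation, implementation and post-implementation periods. Keep the 180-day history requirement and the two 12-month windows of the primary ratio. State how the history requirement works once the index date can fall earlier, so that nobody who now qualifies in a primary window is lost because an earlier prescription lacked 180 days of history.

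Add a note that early-2011 quarters may be thin or unavailable in Spain. Annex 5 says GP data collection there began in 2011 and specialist collection in 2012, so 180 days of prior history cannot exist at the start.

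The cost is a wording change in two places and a wider extraction filter, over a period the study already intends to report.

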This is a post-authorisation, retrospective, observational cohort study using a pre- and post-design to examine the changes in the prescribing patterns. A cohort of patients initiating domperidone will be identified from existing secondary data sources (IMS, CPRD) in selected European Union countries (France, Germany, United Kingdom, Belgium, and Spain). These countries are selected to provide a range of domperidone usage (from France, which has the highest per capita domperidone use in the EU, to Germany, which ranks number 12 in the EU for per capita domperidone use), and based on the availability of robust longitudinal electronic medical records databases. These data sources will include person-level information on demographics, prescriptions, and diagnoses.

Population

Defined as all patients receiving domperidone in the outpatient setting during the pre-defined periods (pre- and post- implementation periods of the risk minimisation activity) in the selected European Union countries (France, Germany, United Kingdom, Belgium, and Spain). Patients will be included in the study cohort if they have at least 1 prescription for domperidone in the selected databases during the pre-defined periods, and have been registered with the practice and have available medical history for at least 180 days.

Variables

Demographic characteristics (including age, sex, and geographic region); indication; dose per day; use in patients with contraindicated conditions; concurrent use with drug that prolong the QT interval or are potent or strong CYP3A inhibitors, and length of treatment will be examined.

Data Sources

Subject to change based on data availability, patient information on domperidone exposure and study endpoints will be obtained from Longitudinal Electronic Medical Records (EMR) databases, including IMS® Disease Analyzer and CPRD. These are described in Annex 5.

Study Size

The study size will vary according to country and data source. All patients available in the study population will be considered for the analysis. Preliminary estimates indicate that the suggested databases capture at least several thousands of domperidone prescriptions in each of the countries being studied.

Data Analysis

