7.2. Background

In 2011, the EU Pharmacovigilance Working Party (PhVWP) recommended that the product information for domperidone-containing medicines should be updated to reflect the risk of adverse cardiac effects of domperidone including QT prolongation, arrhythmias, and sudden cardiac death, and that domperidone should be used with caution in patients with certain heart conditions, including heart failure, a previous heart attack, angina (chest pains), and heart rhythm disorders. In response to this recommendation, the SmPC was updated in 2012 to include QT prolongation as an adverse drug reaction (ADR).

In March 2013, the EMA PRAC initiated a review of domperidone-containing medicines at the request of the Federal Agency for Medicines and Health Products (FAMHP), under Article 31 of Directive 2001/83/EC over concerns about cardiac adverse effects of domperidone. Subsequently, PRAC recommended that the product label (Summary of Product Characteristics/SmPC and Patient Information Leaflet/PIL) of domperidone-containing medicines should be updated to strengthen the information regarding cardiac risks. In addition, PRAC raised concerns that there may be off-label use of domperidone for the stimulation of lactation in breastfeeding women, for the treatment of

gastro-oesophageal reflux disease (GERD), for the treatment of diabetic and non-diabetic gastroparesis, and for the treatment of symptoms of postural hypotension in Parkinson's patients. More recently the EMA asked that IBS be included in the present study as an off-label indication.

The recommended changes following conclusion of the Article 31 referral included the following:

- restriction of the indication to nausea and vomiting;
- limitation of duration of use to 7 days;
- reduction of the maximum daily dose to 10 mg TID for adults and adolescents (12 years of age and older and weighing 35 kg or more);
- reduction of the maximum daily dose to 0.25 mg/kg TID for neonates, infants, children (less than 12 years of age), and adolescents weighing less than 35 kg;
- contraindication of the combination with other drugs that increase the cardiac risks by themselves or increase the plasma level of domperidone; and
- contraindication in patients with moderate or severe hepatic impairment or certain cardiac conditions.

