9.3.6. A Composite Endpoint -All Label Requirements

Each prescription will be classified according to whether it appears to violate at least 1 of the above specifications, i.e., has a presumed indication that is off-label, has a dose that is above 30 mg/day (for ages \geq 12 years) or above 0.75 mg/kg/day (for ages <12 years), is written for a patient with a contraindicated condition, or appears to be prescribed concurrently with a medication contraindicated for concurrent use.

To accommodate the 2 areas of uncertainty described above (1] duration of domperidone use and 2] domperidone prescriptions for which the indication is unknown), the above classification will be done in the following 4 ways to reflect the possible combinations of:

- With consideration of days' supply being more than 7 days;
- Without consideration of days' supply being more than 7 days;
- With classifying subjects with an unknown indication as having an off-label indication; and
- Without classifying subjects with an unknown indication as having an off-label indication

This is described in more detail in Section 9.7.

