9.5. Study Size

The study size will vary according to country and data source. All patients available in the study population will be considered for the analysis. Preliminary estimates indicate that the suggested databases capture at least several thousands of domperidone prescriptions in each of the countries being studied.

Review of domperidone sales data for 2015 from IMS and from the CPRD indicates that the number of prescriptions in each of the databases varies by country. The lowest number of prescriptions was observed in the Belgian database, where the count was 22,000.

Table 2 shows the approximate number of prescriptions for a study with the same number of prescriptions in pre-intervention period and the post-intervention to have 90% power to detect, p<0.05 (2-sided test) risk ratios from 1.1 to 1.4 according to the risk during the pre-intervention period. Note that the "risks" are the probabilities of a prescription meeting the label requirements, so a risk ratio of 1.1 represents a 10% improvement in label compliance when comparing the post-intervention period to the pre-intervention period.

Table 2:Approximate number of Subjects Required per Group (Before Intervention, After Intervention) Under Various Scenarios				
"Risk" of complying with label before	"Risk" Ratio =	"Risk" Ratio =	"Risk" Ratio =	"Risk" Ratio =
the intervention period	1.1	1.2	1.3	1.4
10%	16,000	4,500	2,000	1,200
20%	7,200	1,800	900	500
30%	4,000	1,100	500	300
40%	2,700	700	300	200
50%	1700	500	200	100
60%	1200	300	200	100
70%	700	200	100	100
80%	400	100	100	100

Thus, if compliance with the new label requirements as low as 10% in the pre-intervention period, the study will have \geq 90% power to detect even a risk ratio of 1.1 (a 10% improvement), and smaller improvements would be of limited public health interest. If compliance with the new label is higher than 10% in the pre-intervention period, the study will have \geq 90% power to detect smaller improvements in compliance with the new label. All domperidone prescriptions that are captured during the study period and meet the inclusion criteria will be included in data analysis.

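### The 180-day history rule makes every patient under 180 days old ineligible, yet the label change names neonates and infants and the paediatric results do not state the exclusion

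*Protocol*

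**What the plan says.** Section 9.2.1 opens broadly: "The study population will be defined as all patients receiving domperidone in the outpatient setting during the pre-defined periods". It sets no lower age limit. It then requires "available medical history for at least 180 days before the domperidone prescription". The Abstract carries the same 180-day requirement ("have been registered with the practice and have available medical history for at least 180 days") but does not say from which date the history is counted back. Neither place makes an exception for young children. Section 9.5 ties the analysis to eligibility: "All domperidone prescriptions that are captured during the study period and meet the inclusion criteria will be included in data analysis".

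The measures being evaluated reach the youngest patients. Section 7.2 lists a reduced maximum of "0.25 mg/kg TID for neonates, infants, children (less than 12 years of age"). Section 9.3.6 builds this into the composite endpoint as a dose "above 0.75 mg/kg/day (for ages <12 years"), with no lower age bound. Section 9.7 describes paediatric data separately from adults and adds that the "rate of paediatric use will be calculated as fraction of overall domperidone utilisation". Section 8.2 makes the age of recipients a secondary objective.

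Section 9.9.2 (Limitations) says nothing about the loss of the youngest children.

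**The concern.** The protocol's scope and its entry rule disagree. The scope includes neonates and infants, by name in the label change and by implication in the dose component. The entry rule removes everyone below 180 days of age by construction, whatever the quality of their records.

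Two things are at stake. First, the study would give no evidence on whether prescribing to neonates and young infants follows the new label, although the measures address them expressly. Second, a reader of the final report would take the paediatric tables and the paediatric fraction to cover all children, because nothing in the protocol says otherwise.

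This cannot be left to a statistical analysis plan, because the protocol itself fixes eligibility.

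**Working it through.** **Who is excluded.** History before a prescription cannot be longer than the patient's age at that prescription. At least 180 days of history therefore requires an age of at least 180 days.

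- 180 / (365.25/12) = 5.91 months; 180/7 = 25.7 weeks.
- A neonate (up to 28 days, assumed as the usual definition) has at most 28 days of history, and 28 < 180, so no neonate qualifies.
- Share of the first year of life removed: 180/365.25 = 49.3%.
- Share of the 0 to <12 year age range removed: 180/(12 × 365.25) = 4.1%. These are shares of age, not of prescriptions. The protocol gives no prescription counts by age.

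**Which prescription the rule refers to.**

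- If it applies to each prescription, every prescription before day 180 is lost.
- If it applies at the index date (the first prescription in the study periods), a child first prescribed at 3 months fails entry, and later prescriptions may be lost too.
- Only a loose reading lets early prescriptions back in. It takes the Abstract's wording, which does not fix the date, together with the statement in 9.9.1 that all prescriptions of eligible patients count. The text of 9.2.1 does not favour that reading.

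**What the look-back is used for.** The diagnosis windows in 9.3.2 and 9.3.4 are 7 days and 2 months (indication), 30 days and 6 months (cardiac contraindication), and from 1 January 2011 (hepatic contraindication). If an infant's practice record starts at birth, each window is covered by that record as far as the infant's life extends. The plan already accepts unequal look-back, since 180 days of history does not guarantee coverage back to 2011 for anyone older.

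**Effect on the paediatric fraction.** Let f be the true paediatric fraction, s the share of paediatric prescriptions the rule removes, and a the share of adult prescriptions it removes through short history. The protocol gives none of the three, so all values below are assumptions.

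Observed fraction = f(1−s) / [f(1−s) + (1−f)(1−a)]

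| f | s | a | Observed fraction |
|---|---|---|---|
| 20% | 25% | 0% | 15/95 = 15.8% |
| 20% | 25% | 10% | 15/87 = 17.2% |
| 20% | 25% | 25% | 15/75 = 20.0% |
| 20% | 5% | 10% | 19/91 = 20.9% |

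The fraction is too low if s > a, unchanged if s = a, and too high if s < a.

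**The case against.** A uniform look-back is an ordinary design choice, and several points against a stronger claim are sound.

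- **Direction of bias.** A reader might infer that the paediatric fraction must be biased downwards. That holds only if the rule removes no adult prescriptions, or proportionately fewer adult than paediatric ones. It applies at every age and so also removes older patients new to a practice. The table shows the error can vanish or reverse.
- **Complete look-back from birth.** A reader might infer that an infant known to a practice since birth is fully observed. Section 9.9.2 says that diagnoses and co-medications are missed when a patient attends several physicians. Annex 5 describes the Belgian source as general practitioners only, and its list of French specialties does not include paediatrics. A record from birth is not a complete record. The plan accepts this weakness at all ages, however, so it does not justify excluding only the youngest.
- **Primary result.** The same rule applies in both periods. Nothing in the protocol shows that it biases the within-country risk ratio among included patients.
- **Feasibility.** The protocol refers to registered patients for the UK source (9.4), but Annex 5 describes the other four as office-visit records and mentions no birth-registration field.
- **Dose data.** Under 9.3.3, the mg/kg dose uses a weight from up to 1 year before the prescription. For a young infant that could be a birth weight, or no weight may exist, and 9.7 does not impute missing values.

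These points limit the consequences and the ease of the remedy. They do not remove the mismatch between scope and eligibility, or the silence about it.

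**Conclusion.** The point holds as a coverage gap. As 9.2.1 is written, patients under 180 days old are ineligible. This follows from the rule alone and needs no assumption beyond reading 9.2.1 as it stands. The paediatric results then describe children of about 6 months and over, and the protocol does not say so.

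The number of prescriptions lost cannot be derived from the document, nor can the size or net direction of any error in the paediatric fraction. There is no ground for saying that the primary risk ratio is biased for the patients included. The gap is worth correcting because the measures under evaluation name the excluded group and the correction is modest, but it does not threaten the main comparison.

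**What to change.** Add to 9.2.1, and mirror in the Abstract: for a patient under 180 days old at the prescription, the history requirement is met if the practice record begins at birth or within a short fixed period of birth, with that period stated. Report this age band separately, so that its shorter look-back does not blend into the other paediatric results.

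Where a database cannot identify a record that begins at or near birth, keep the 180-day rule for that country. In that case state the exclusion in 9.9.2 and label the paediatric results and the paediatric fraction as age 180 days and over.

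The cost is a short protocol change, an extra condition in the extraction and a feasibility check in each database. The added band will have a shorter look-back that may miss diagnoses recorded elsewhere, and weights for the mg/kg dose may be missing or outdated. Separate reporting keeps both problems visible.
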